Uniformity of the intervention within and across the sites is critical. Standardization of staff training procedures has been identified for two main areas: 1) EAW components for the home evaluation, companion interview, ReWalk fitting, EAW Basic Skills Test, EAW walking skill progression, EAW walking test evaluations, EAW Advanced Skills Test, and EAW Activity Log; and 2) administration of the outcome assessments for the VR-36, SCI-QOL, Global Impression of Change Scale, PROMIS Sleep Disturbance, Bowel function, and SCI-FI. Onsite training of procedures will be conducted at each site in order to standardize EAW training techniques across the sites. The ReWalk Trainers will be required to demonstrate knowledge and capability to perform the required procedures related to the EAW training and assessments. The Study Coordinator at each site will be responsible for the QOL outcome assessments. This strengthens the study because the staff persons providing the intervention are not the ones performing the outcome assessments.

VIII. DETERMINING ELIGIBILITY

The determination of eligibility for this study has several levels. First, the Site Physician will pre-screen potential participants from the medical records and knowledge of the person to include those with traumatic or non-traumatic, complete or incomplete SCI duration ≥ 6 months who are ≥ 18 years old and are wheelchair-dependent for indoor and outdoor mobility.

Second are the Screening evaluations; those potential participants who pass pre-screening and are interested to be consented will begin the consenting process with the Site Physician and site study team. Those who complete the consenting process will undergo a series of screening evaluations that include: a BMD scan, fracture history, lateral foot x-rays of each calcaneus, history and physical examination and ISNCSCI assessment to determine medical wellness, anthropometric compatibility with the device, level and completeness of injury, hand function, ability to have a companion, and a home evaluation for suitability. Female participants will also receive pregnancy testing. The specific inclusion and exclusion criteria are itemized below.

A. Inclusion/Eligibility Criteria

Veteran/Active Duty Participants:

1. Veterans or active duty military personnel who are at least 18 years of age;
2. Traumatic or non-traumatic SCI ≥ 6 months duration of SCI;

3. Wheelchair-user for indoor and outdoor mobility;

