Intervention Group: Training for the Intervention group will consist of 25±5 sessions of EAW training followed by an EAW Advanced Skills Test that will determine the eligibility of the participant to take the device home. Training will take place at the VA hospitals, in the CBOCs under the same FWA as the sites, or in the participant's home/community. Participants in the Intervention arm will take the device home to use. During the training and home/community use components of the study, the built-in step counter on the device will record the weekly total number of steps taken. The EAW Activity Log will be completed by each participant on a weekly basis to record the location, duration and frequency of device use. The Trainers will follow up weekly with the participants for completion of this task.

Control Group: In order to provide a similar level of attention to the Control group during the Orientation/Training phase, the Control group will receive interviews to identify types of physical activities in which they usually participate. Control participants will be instructed to complete the Usual Activity Log on a weekly basis during the Orientation/Training course and during the four-month Intervention phase. Weekly contact by the study team will be provided to the Control group during the Orientation and Intervention phases, in person, over the phone, or through secure messaging using My HealtheVet.

IX. OUTCOME MEASUREMENTS

The frequency and specific time points of each of the outcome measurements can be found in the "Training and Testing Schedules" (Table 6).

The two primary, major secondary and secondary outcomes are measured at baseline, post Orientation/Training phase, post 2-month Intervention phase, and post 4-month Intervention phase. The main comparison for the two primary and major secondary outcomes is the change in

the outcome measures from baseline to post 4-month Intervention phase.

A. Primary Outcomes

1. Mental Health Component Summary (MCS) of the Veterans Rand-36 (VR-36) for Vitality, Social Functioning, Role-Emotional, and Mental Health.
2. The sum T-score for the SCI-QOL Physical Medical Health domain (three item banks of Bladder Management Difficulties, Bowel Management Difficulties, and Pain Interference).

B. Major Secondary Outcome

1. Total body fat mass (by DXA scan) (results will be blinded)

C. Secondary Outcomes

1. Global Impression of Change Scale (Participant- and Companion-rated);

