 - c. Walk tests and mobility assessments are recorded during each session once the participant is able to perform them and for the duration of the Training phase for the:
 - i. 10 meter walk test for time (10mWT),
 - ii. 6 minute walk test for distance (6minWT), and
 - iii. Timed-up-and go (TUG).
 - d. Walk tests and mobility assessments are recorded at months 2 and 4 during the Intervention phase as an outpatient visit.
3. Exit survey: participants and companions will be asked questions about their satisfaction with the study overall, and specifically about the device and training.
 - a. Previously randomized participants and their companions will be called to complete the "Exit Survey".

F. Methods for Obtaining Outcome Measures Data

The Site ReWalk Trainers and Assistant ReWalk Trainers will perform the mobility skills and walking tests and be responsible for recording the EAW data. Exoskeletal-assisted mobility walking test assessments are measured in distance and/or time. Other mobility skills such as arresting gait on command, maneuvering to a wall rest, navigating doors, etc., will be scored one session per week as “able” or “unable” to perform the task; in addition, the level of assistance needed to complete the task will be recorded with each assessment.

The Site Coordinator will be responsible for administering the QOL outcome assessments (VR-36, SCI-QOL, Global Impression of Change Scale (Participant- and Companion-rated), PROMIS Sleep Disturbance, SCI-FI, and bowel function surveys) through in-person or phone interviews. The Site Coordinators will record all answers on the fixed forms. The site Trainers may assist as back-up QOL assessors only if necessary. In order to have continuity of assessment, the Site Coordinators will administer the surveys at all of the time points. Each SCI-QOL, PROMIS Sleep Disturbance and SCI-FI survey is reported as a T-score (mean=50, SD=10). The VR-36 is in a fixed form and administered sequentially.

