The proposed study will require fifteen sites. Each site will have four full time staff who would be solely dedicated to the conduct of the study (1 ReWalk Trainer, 2 Assistant ReWalk Trainers and 1 Study Coordinator). Two staff persons are needed during the initial EAW Training phase for each of the participants. The ReWalk Trainer will have a clinically relevant professional background such as a biomedical, electrical or mechanical engineer, physical therapist, exercise physiologist, occupational therapist, nurse, athletic trainer, or equivalent. The ReWalk Trainer will be responsible for the screening of participants, scheduling, fitting and training of the exoskeleton, and mobility measurement aspects of the protocol. The ReWalk Trainer and Assistant ReWalk Trainers will be responsible for the administrative paperwork, assist with eligibility screening, assist with the informed consent process, scheduling of participants, the home evaluation when needed, the EAW training, weekly and monthly participant contact during the orientation and home use phases of the study, ensuring the Usual Activity log and EAW Activity Log are completed, reporting adverse events, and all other aspects of the study protocol. The Assistant ReWalk Trainers will assist the trainer in all EAW aspects of the study. All of the Trainers must be capable of assisting with the EAW training and as such, are expected to be healthy and free of back or other medical problems that would be contraindicated for lifting and carrying 60 pounds across a room. The Trainers must be able to lift the exoskeleton from one chair to another, or to place one in or take it out of the trunk of a car or van.

CS #2003 study will also support a Site Coordinator. The Site Coordinator will be responsible for the administration of the QOL outcome surveys, local Research & Development and CIRB application paperwork and assisting with scheduling and data entry. The study Coordinators may

be physical therapists, PT assistants, exercise physiologists, nurses, nurse assistants, research health science specialists or technicians, or other comparable disciplines that have experience with research methods and procedures and experience and knowledge about persons with SCI. Approved and classified PDs will be provided to the sites for recruitment of study personnel if requested.

Each Site will need the following:

1. Access to a bone mineral densitometer or space for the ones to be provided by CS #2003;

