QOL outcome assessments (VR-36, SCI-QOL, Global Impression of Change Scale (Participant- and Companion-rated), PROMIS Sleep Disturbance, SCI-FI, and bowel function surveys) will be completed by each participant during an in-person or phone interview by a member of the study site staff. The interviewer will record the answers, making sure that all questions are answered. This data will be sent to the CSPCC via a Datafax system.

XVII. PLANS FOR DISSEMINATION OF STUDY RESULTS

A. Publication of Research Results

It is the policy of the Cooperative Studies Program not to reveal outcome data to Site Investigators until the data collection period of the study is complete. This policy is meant to prevent possible biases that might affect data collection. Members of the DMC will be reviewing outcome results to ensure that the study will be terminated early if a treatment is identified as prohibitively dangerous or if a definitive answer is reached prior to the scheduled study termination date.

All presentations and publications resulting from this study will follow CSP policy as specified by the CSP guidelines. The presentation or publication of any or all data collected by Site Investigators on patients entered into a Department of Veterans Affairs Cooperative Study is under the direct control of the study's Executive Committee. No individual Site Investigator has the right to use the study's data to perform analyses or interpretations, or to make public presentations or seek publication of any or all of the data without specific approval of the Executive Committee.

The Executive Committee has the authority to establish any number of publication committees, which usually will comprise of subgroups of Site Investigators and some members of the Executive Committee, for the purpose of producing manuscripts for presentation and publication. Any presentation or publication related to this study should be circulated to the Executive Committee for review, comments and suggestions at least four weeks prior to submission of the manuscript to

the presenting or publishing body.

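### Trainers may stand in as interviewers for both primary outcomes, so the stated separation of treatment from assessment does not hold as written

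*Combined protocol and SAP*

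**What the plan says.** Section VII (uniformity of intervention) assigns the role: "The Study Coordinator at each site will be responsible for the QOL outcome assessments". It then draws a design claim from this, without exception: "This strengthens the study because the staff persons providing the intervention are not the ones performing the outcome assessments".

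Section IX.F (methods for obtaining outcome data) also gives the Coordinator the QOL battery. Its list opens with the VR-36 and SCI-QOL and ends "Global Impression of Change Scale (Participant- and Companion-rated), PROMIS Sleep Disturbance, SCI-FI, and bowel function surveys) through in-person or phone interviews". It then adds "The site Trainers may assist as back-up QOL assessors only if necessary", and goes straight on to say "In order to have continuity of assessment, the Site Coordinators will administer the surveys at all of the time points".

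Section XVI (data management) says the same instruments "will be completed by each participant during an in-person or phone interview by a member of the study site staff", with the interviewer writing down the answers. Section XV likewise refers only to the site's study staff.

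On the Trainers, Section XIV.A says: "The ReWalk Trainer will be responsible for the screening of participants, scheduling, fitting and training of the exoskeleton, and mobility measurement aspects of the protocol". For the weekly device-use log in the Intervention arm, Section VIII.I says: "The Trainers will follow up weekly with the participants for completion of this task".

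**The concern.** Both primary outcomes are self-reports given aloud to an interviewer, by participants who know which arm they are in. The protocol describes no blinding of the QOL interviewer. In Section IX, blinding of results is mentioned for total body fat mass and lipids, not for the two primaries. Keeping the interviewer apart from treatment delivery is the protection that Section VII offers, and the back-up rule takes it away without saying so.

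A participant asked about mood, bowel, bladder and pain by the person who taught them to walk in the device may be inclined to answer kindly. Each primary is a threshold (a gain of at least 4.0 points on the MCS, or at least 10% on the SCI-QOL sum), so a modest shift in answers can turn a failure into a success. Baseline assessment precedes all exoskeleton training (Section III.A). A Coordinator at baseline and a Trainer at month 4 would therefore place a change of assessor inside the change score.

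**Working it through.** **1. The plan's own figures.** This point challenges no number. Table 7 reproduces exactly with the continuity-corrected two-proportion formula (two-sided alpha 0.025, control 0.10):
- MCS (0.333, 80% power): 67 per group; 67/0.85 = 78.8, so 79.
- SCI-QOL (0.42, 95% power): 60 per group; 60/0.85 = 70.6, so 71.

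**2. The texts side by side.**

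| Section | Who takes the QOL interviews |
|---|---|
| VII | Coordinator; intervention staff do not assess |
| IX.F, back-up sentence | Trainers, if necessary |
| IX.F, next sentence | Coordinators, at every time point |
| XV and XVI | Site staff, role not specified |

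These cannot all be true. The documents do not define when back-up is necessary, set no limit on it, and plan no analysis by interviewer (Sections XIII.F and XIII.G).

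**3. How likely is back-up use?** Section XIV.A gives each site one Coordinator and three Trainers (one ReWalk Trainer, two Assistants). No other back-up interviewer is named, so a Coordinator absence points to a Trainer. No frequency is given.

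**4. Trainer contact by arm.**
- Both arms: five basic exoskeleton sessions before randomization (Section III.A), and Trainer responsibility for weekly and monthly contact during the orientation and home-use phases (Section XIV.A).
- Intervention arm only: 20 to 30 further training sessions (Section VI), weekly follow-up on device use (Section VIII.I), and walk tests at months 2 and 4 done by Trainers (Sections IX.E and IX.F).

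Exposure is unequal, but it is not confined to one arm.

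**5. Illustration of size.** The share and lift below are assumptions, not document figures. Suppose there is no true effect and success is 10% in both arms. Let s be the share of Intervention interviews done by Trainers and b the rise in reported success in those interviews, with no rise in Control. Then:

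p_I = 0.10 + s × b, p_C = 0.10, n = 80 per arm.

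The test is the uncorrected chi-square, z = (p̂_I − p̂_C) / √[2 p̄(1 − p̄)/80], rejecting when |z| > 2.241 (two-sided 0.025). The rejection probability is the exact binomial sum over all pairs of counts.

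| Trainer share s | p_I at b = 5 / 10 / 20 points | Rejection at b = 5 / 10 / 20 points |
|---|---|---|
| 0 | 10% | 2.2% |
| 10% | 10.5 / 11 / 12% | 2.3 / 2.5 / 3.3% |
| 25% | 11.25 / 12.5 / 15% | 2.7 / 4.0 / 9.4% |
| 50% | 12.5 / 15 / 20% | 4.0 / 9.4 / 31.7% |

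In counts, s = 10% and b = 20 points means 8 interviews and 8 × 0.20 = 1.6 extra successes among 80. The hypothesized differences are 23.3 points (0.333 − 0.100, or 18.6 of 80) for the MCS and 32 points (0.42 − 0.10, or 25.6 of 80) for the SCI-QOL.

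The illustration treats all 80 as interviewed. With 15% dropout counted as failure, the shift would be 0.85 times as large. Assuming some lift in Control as well would shrink it further.

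**The case against.** The strongest reply is that this is a narrow wording conflict with little behind it. Back-up is for necessity only, the adjacent sentence expects Coordinators throughout, answers go on fixed forms, staff training in administering these instruments is standardized, and the Co-National Coordinator visits yearly to check QOL standardization. At a 10% Trainer share the table moves from 2.2% to at most 3.3%. Larger inflation needs a share that is hard to reconcile with a back-up role. All of that stands, and it limits the size of the concern. It does not make the claim in Section VII true, and nothing in the plan holds use to a low level or commits to reporting it.

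It is also true that Coordinators are not described as blinded. They may take activity-log information (Section V) and reschedule missed sessions (Section VI). Barring Trainers restores the separation but leaves participants and interviewers aware of allocation.

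Four stronger readings are tempting and are not supported:
- *The bias arises only in the Intervention arm.* Controls also have five exoskeleton sessions and Trainer contact, so only a likely imbalance can be claimed.
- *Every Trainer has spent 20 to 30 sessions with each Intervention participant.* Sites have three Trainers, and no section says that each attends every session.
- *The success rate is inflated by a known amount.* Both the share and the lift are assumed; even the direction is inference.
- *The interviewer is not recorded.* The case report forms are not part of the documents, so this cannot be judged.

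**Conclusion.** Wrong as written: Section VII asserts a separation that Section IX.F removes and Sections XV and XVI do not protect, for the interviews behind both primary outcomes. This rests on the text alone and is certain.

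The consequence is much less certain. Any courtesy bias is likely to be stronger in the Intervention arm because Trainer contact is far greater there, but its size cannot be estimated from the documents. Under the assumptions above it is small if Trainers interview rarely and could matter if they did a quarter or more of the Intervention interviews with a large lift. The documents give no evidence that Trainers did so. The point deserves correction because the exposed endpoints are the primaries and the repair is modest. It is not a reason to discount the trial.

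**What to change.** - Reconcile Sections VII, IX.F, XV and XVI so that Trainers do not conduct VR-36 or SCI-QOL interviews after randomization.
- When the Coordinator is unavailable, reschedule within the visit window (the protocol allots one week to the post-intervention evaluations), or use an existing non-Trainer by telephone, which is already a permitted mode. Chair's Office national coordinator staff are full time (Section X.B). If the Co-National Coordinator interviews, someone else should monitor those interviews. A Coordinator from another site is less clean, because contact data are held within each site (Section XV).
- Record the interviewer's role on each QOL form, if it is not already there.
- Report the number of Trainer-administered primary assessments by arm and time point.
- Pre-specify a sensitivity analysis of both primaries: count Trainer-administered month-4 successes as failures and, separately, exclude those assessments. Exclusion departs from ITT, so the planned ITT analysis stays primary.

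Cost: a protocol amendment with Central IRB review, access arrangements for any off-site interviewer, occasional scheduling effort, and some loss of interviewer continuity when a back-up is used. No new staff are needed. This is version 7.2 (July 2021), and Table 5 ends enrollment in FY20 with carry-over and close-out in FY21. If few interviews remain, the interviewer record, the count by arm and the sensitivity analysis carry most of the value, provided interviewer identity can be recovered.
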